466 regions. Participating paramedics will be trained in this algorithm before recruitment commences, with a refresher at
467 the mid-point of patient enrolment. The use of such an algorithm reflects routine practice, in that paramedics will
468 usually follow a specified protocol or “airway ladder” when managing the airway during OHCA. This approach will
469 standardise care in each trial arm, and all other elements of the care pathway will be identical.
470

471 Care will proceed as normal for OHCA patients enrolled in the trial, aside from the initial airway management. All
472 other interventions will proceed according to standard resuscitation guidelines that are disseminated widely in the
473 United Kingdom and internationally.
474

475 Patients who die at the scene will be managed in accordance with nationally disseminated ambulance service protocols
476 (e.g. recognition of life extinct, or confirmation of death). The remaining survivors will be transported to hospital, with
477 approximately half of these admitted to an intensive care unit (ICU). These patients will be treated using standard post-
478 OHCA care pathways.
479

480 **4.6 Primary and secondary outcomes**

481

482 **4.6.1 Primary outcome**

483

484 The primary outcome will be the modified Rankin scale (mRS) score measured at hospital discharge. However if the
485 patient remains in hospital for more than 30 days after the OHCA, the primary outcome (mRS) will be assessed at the
486 30 day time point instead of at discharge. The mRS which incorporates survival to discharge is widely used in OHCA
487 research[28, 29]. mRS is usually presented dichotomously as good recovery (0-3) or poor recovery/death (4-6).

488

489 All enrolled patients are eligible. We will collect survival data and mRS at hospital discharge with the prior
490 permission of the Health Research Authority Confidentiality Advisory Group (CAG), thereby ensuring close to 100%
491 data ascertainment.

492

493 For patients that survive to hospital discharge (or are still inpatients 30 days after their OHCA) the mRS will be
494 determined by a research nurse who will assess the patient using a simple flow chart that has been previously used to
495 assess patients who have had a cardiac arrest[30]. Any patient who does not survive to discharge will automatically be
496 assigned a score of six (dead) .

497

498 **4.6.2 Secondary outcomes**

499

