1231 after at approximately 24 hours have elapsed, to take written informed consent if the patient decides to participate. The
1232 name and address of those who consent to active follow-up will be captured at this time.

1233

1234 There will be 3 different consent options:

1235

1236 A. The patient can consent to ACTIVE follow-up; where both routine data sources will be used and the patient
1237 will be actively followed up at discharge, 3 and 6 months after the index OHCA. Quality of life and mRS
1238 score will be collected at these time points.

1239

1240 B. The patient can consent to passive follow-up; with this option only routine data will be collected and the
1241 patient will not be contacted again about the study.

1242

1243 C. If a patient does not wish to be followed up they can select the option; I decline to take any further part in the
1244 study. I do not wish to be contacted again (with this option no further data collection will take place).

1245

1246 We will ask all OHCA survivors to sign the consent form, selecting which method of follow up they would prefer
1247 (three different options on the consent form). Patients will be given a copy of the consent form for their own records,
1248 one copy will be placed in the patient's medical records and the original copy will be kept in the secure study records.

1249

1250 If a patient does not wish to complete the consent form a record of this will be taken and these patients will
1251 automatically be assigned to option C where no further data collection will take place.

1252

1253 In the rare event of a patient with capacity being unable to physically complete the consent form, verbal consent will
1254 be accepted and will be documented on the study specific consent form and in the medical notes. An independent
1255 member of staff (e.g. a registered nurse caring for that patient) will be asked to annotate the consent form to indicate
1256 that they have witnessed verbal consent.

1257

1258 There will be a few cases where patients are discharged from hospital (either to another facility or their usual place of
1259 residence) before the consent process can be completed. We will post a PIL to these patients, with a covering letter,
1260 patient consent form. We will provide contact details of the local research nurse so that the patient can easily contact
1261 someone if they have any questions about the study.

1262

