1712 commenced or continued by ambulance staff or responder. For specific inclusion/exclusion criteria and details
1713 of study patients and paramedics see template **Figures F1** and **F2**. 'Trial patients' are those who are
1714 resuscitated, attended by an A2 paramedic and meet the eligibility criteria.

1715 Recruitment over time against targets will be presented by trust and overall (**Figures F3, F4 and F5**).

1716 In the context of this trial, 'advanced airway management' refers to the use of intubation, the i-gel device or
1717 other supraglottic airway devices.

1718 **3.1 Consent**

1719 Due to the emergency nature of the trial, we have ethical approval to enrol patients without consent and seek
1720 consent for further participation from patients who survive to discharge from intensive care (ICU). We have
1721 approval to retain data collected up to the point of approach (or death if this occurs before approach) as well
1722 as mRS at hospital discharge or death for all patients regardless of whether they consent.

1723 Patients may choose one of the following three options when presented with the trial information and consent
1724 form:

1725 Active follow-up - Routine data will be utilised and the patient will be actively followed up at hospital
1726 discharge, and 3 and 6 months after the index OHCA. Quality of life and mRS will be collected at these three
1727 time points.

1728 Passive follow-up - Only routine data will be collected and the patient will not be contacted again about the
1729 study.

1730 Does not wish to participate – No further data collection will take place.

1731 **3.2 Flow of participants**

1732 Participant and paramedic flow will be described via flowcharts (see **Figures F1** and **F2**). Follow-up will
1733 occur at three and six months post OHCA (target ± 4 weeks) for patients who consent to active follow-up.

1734 **3.3 Characteristics of non-study patients**

1735 All resuscitated patients who are attended by an A2 paramedic and meet the eligibility criteria are
1736 automatically enrolled in the study and classed as trial patients. Key demography and initial cardiac arrest
1737 details are collected for all resuscitated patients, including those who are not attended by an A2 paramedic or
1738 are ineligible; these details will be described for trial and non-trial patients (**Table T1**). Resuscitated non-trial
1739 patients are referred to as population 0 in this document.

1740 **3.4 Randomisation**

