1791 analyses on an intention to treat basis (ITT). For patients who do not wish for their previously collected data
1792 to be used, we will exclude all data collected after the point of consent (i.e. ward movements, EQ-5D and
1793 follow-up data) from any analyses.

1794 Data on all withdrawals is captured on a specific case report form (CRF), and will be tabulated by allocation
1795 of the enrolling paramedic (**Table T3**).

1796 **3.7 Analysis populations**

- 1797 • **Population 1a:** The analysis population for the primary outcome (mRS at discharge/30-days) is all
1798 patients who receive resuscitation, are attended by an A2 paramedic and meet the eligibility criteria,
1799 i.e. all trial patients. This is also the analysis population for outcome 5 (chest compression fraction),
1800 but limited to two trusts and starting partway through the trial.

- 1801
- 1802
- 1803
- **Population 1b:** The analysis population for the second component of secondary outcome 6 (ROSC on ED arrival) is all patients who receive resuscitation, are attended by an A2 paramedic, meet the eligibility criteria and were conveyed to ED.
- 1804
- 1805
- 1806
- 1807
- **Population 2:** The analysis population for secondary outcomes 1 to 4, 6 and 7 (airway management details, but only covering ROSC during advanced airway management by A2 paramedic for outcome 6) is all trial patients who received at least one advanced airway management attempt by the enrolling A2 paramedic.
- 1808
- 1809
- **Population 3:** The analysis population for secondary outcome 8 (length of initial ICU stay) is all trial patients who were admitted to ICU.
- 1810
- 1811
- 1812
- **Population 4:** The analysis population for secondary outcome 9 (length of hospital stay) is all trial patients admitted to hospital who did not refuse consent (i.e. patients who either consent to active or passive follow-up or who die prior to approach).
- 1813
- 1814
- 1815
- 1816
- 1817
- **Population 5:** The analysis population for secondary outcomes 10 and 13 (EQ-5D health scores and state scores) and secondary outcomes 11 and 12 (time to death after discharge and mRS during follow-up) is all trial patients who consent to active follow-up, survive to 30 days/hospital discharge and provide relevant data for at least one of the three time points (30 days/hospital discharge, 3 months and/or 6 months).
- 1818
- 1819
- 1820

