Was there bystander cardiopulmonary resuscitation (CPR)?	Form B (minimal dataset/CAD) Form E1 (paramedic)	1. Form E1 2. Form B
Date and time of hospital admission/emergency department (ED) admission	Form D (minimal dataset/paramedic contact) Form E1 (paramedic) Form G (hospital staff)	1. Form G 2. Form E1 3. Form D

1833

1834 **5. DERIVATIONS**

1835 **5.1 Primary outcome**

1836 To be calculated for all patients in population 1. Modified Rankin Score (0 to 6) at hospital discharge (or 30
1837 days post-OHCA if the patient is still in hospital at that time) is recorded for all patients who survive to
1838 hospital discharge (or 30 days post-OHCA). All trial patients who do not survive to hospital discharge (or 30
1839 days post-OHCA) will be assigned a score of 6 (dead). mRS will be dichotomised and analysed as good
1840 recovery (score 0 to 3) compared to bad recovery/death (score 4 to 6).

1841 Note. mRS is also collected at 3 and 6 months post-OHCA for patients who consent to active follow-up and
1842 will be used to calculate a dichotomised score as above and utilised for the secondary outcome of mRS up to
1843 6 months.

1844 **5.2 Compression Fraction**

1845 The compression fraction (expressed as a percentage) is measured by placing a credit-card-sized CPRCard
1846 device (Laerdal Medical, Stavanger, Norway) on the patient's chest during CPR to collect chest compression
1847 data. Data are downloaded from the card and interpreted using a CPRCard Laerdal Card reader ID CPR30-
1848 LA (FEIG Electronic, Germany) and a standard algorithm.

1849 **5.3 EQ-5D**

1850 To be calculated for all patients in population 5 at up to three time points: hospital discharge/30days post
1851 OHCA, 3 months post OHCA and 6 months post OHCA.

1852 A five digit 'state' score will be derived from the mobility, self-care, usual activities, pain/discomfort and
1853 anxiety/depression scores using the following:

1854 State = 10000*mobility score + 1000*self-care score + 100*usual activities score + 10*pain/discomfort score
1855 + anxiety/depression score

1856 Each state will then be assigned a single summary index score according to a standard scale. These index
1857 scores are numerical and range from -0.59 to 1.00, with a score of 1.00 denoting perfect health. If any of the
1858 five raw scores are missing, the state score and index score will be missing.

1859 The EQ-5D questionnaire visual analogue scales are also collected. Such scores range from 0 to 100 (with

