Time to death	
If survival status=died prior to hospital discharge & consent status≠active and status≠passive, then = 12 midnight
 
If survival status=survived to 30 days/hospital discharge & has patient died since hospital discharge=Yes, then = 12 midnight
 
(we do not collect time of death for patients who died after ICU discharge and do not consent to any follow-up or for patients who consent to active follow-up but died after hospital discharge)
 
Else missing
 
For patients who die prior to admission, in hospital, or during the follow up period:
 
(Date of death – Incident date (Form A))*24*60 + (Time of death – Incident time (Form A))
 
For patients who survive to 30 days/hospital discharge & consent to active follow-up and provides 6 month follow-up data (i.e. censored at 6 months post discharge for analysis)=
 
(6m follow-up date (Form K-Cover) - Incident date (Form A)) *24*60 + (12 midday - Incident time (Form A))
 
For patients who survive to 30 days/hospital discharge & consent to active follow-up and provides 3 month follow-up data but not 6 month follow-up data (i.e. censored at 3 months post discharge for analysis)=
 
(3m follow-up date (Form K-Cover) - Incident date (Form A)) *24*60 + (12 midday - Incident time (Form A))
 
For patients who survive to 30 days/hospital discharge & consent to passive follow-up or consented to active follow-up but do not provide any 3 or 6 month data (i.e. censored at hospital discharge for analysis)=
 
(Hospital discharge date (Form H/I3) - Incident date (Form A)) *24*60 + (Hospital discharge time (Form H/I3) - Incident time (Form A))
 
For patients who survive to (30 days or) hospital discharge & did not consent to active or passive follow-up (i.e. censored at ICU discharge for analysis) =
 
(ICU discharge date (Form G) - Incident date (Form A)) *24*60 + (ICU discharge time Form G) - Incident time (Form A))
 
Note – if time to death exceeds 183 days, then it will be censored at 183 days

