1916 intervals (95% CI). .

1917 • **Continuous outcomes** will be summarised by means and SDs in each treatment group, if distributions
1918 are approximately normal. If distributions are non-normal data will be summarised by the median and
1919 IQR or geometric mean (GM) if a logarithmic transformation provides an approximately normal
1920 distribution. Outcomes will be compared using linear regression. For untransformed data treatment
1921 comparisons will be presented as adjusted differences in means with 95% CI, and for logarithmically
1922 transformed data as adjusted ratios of GMs with 95% CI. Due to the large numbers of trial patients not
1923 expected to survive to 30 days/hospital discharge, a two-part zero-inflated modelling approach will also
1924 be considered for EQ5D visual analogue scale and summary index scores. This will comprise a) an
1925 occurrence model, a logistic regression model for the occurrence of death vs survival; b) intensity model,
1926 a log-linear model for the score, conditional on survival. If it is not possible to fit the model, then an
1927 analysis restricted to those who survive to hospital discharge will be considered.

1928 • **Time to event outcome** time to death will be summarised by the median and IQR in each intervention
1929 group. This will be compared using Cox's proportional hazards or parametric models as appropriate. The
1930 choice of model to use will depend on the distribution of the data. The intervention comparison will be
1931 presented as a hazard ratio (HR) and 95% CI if a proportional hazards model is used or time ratios (TR)
1932 and 95% CI if an accelerated failure time (AFT) model is used. Times will be censored at last contact for
1933 patients known to be alive at that time.

1934 • **Longitudinal outcomes** will be summarised for each time point. Binary and continuous outcomes will
1935 be compared using logistic and linear mixed effects methodologies respectively, with the treatment group
1936 and study design variables (see section 6.2.1) fitted as fixed effects, and patient terms as random effects.
1937 If a time x treatment interaction is not statistically significant at the 10% level an overall treatment effect
1938 will be reported. If the interaction is statistically significant the changes in treatment effect with time will
1939 be described. Different variance/covariance structures will be explored, and the structure that provides

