- 1972 There will be no missing data for any of the randomisation factors (by design).
- 1973 Missing outcomes:
- 1974
 - If the proportion of missing data is less than 5% then complete case analysis will be performed (i.e.
1975 excluding cases with missing data).
 - If the proportion of missing data is above 5% multiple imputation methods will be considered. A general
1976 imputation model that uses an iterative procedure to generate imputed values will be used to generate
1977 multiple complete data sets (e.g. using Stata’s mi impute). The model of interest will be the fitted to each
1978 of the complete data sets and effect estimates combined using Rubin’s rules.
- 1979
- 1980 If appropriate (the level of missingness is >20%) then any variables that are predictive of missingness will be
1981 identified, and if there is reason to suggest that an assumption of missing at random (MAR) given these
1982 variables is reasonable then such variables will be adjusted for in the models of interest. These models can be
1983 shown to provide unbiased estimates of the treatment effect and moreover multiple imputation approaches
1984 would not be expected to recover any additional information.
- 1985 **6.2.8 Multiple testing**
- 1986 No formal adjustment will be made for multiple testing. However as previously described formal statistical
1987 comparisons will not be made for outcomes with low event rates and only pre-specified subgroup analyses

1988 will be performed. Consideration will be taken in interpretation of results to reflect the number of statistical
1989 tests performed and the consistency, magnitude and direction of treatment estimates for different outcomes.

1990 **6.3 Safety data**

1991 Safety data are only collected for events which are unexpected and potentially related to the intervention. All
1992 such events will be detailed along with descriptions of patients' airway management pathway. **Table T9**
1993 summarises such events, as captured via serious adverse event (SAE) report forms and full details will also be
1994 given as listings (see **Table T10**).

1995 No formal comparisons between groups will be made as numbers of events are expected to be small.

1996

1997 **7. AMENDMENTS TO THE SAP**

Previous version	Previous date	New version	New date	Brief summary of changes

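### The 5% complete-case rule is too loose for a primary mRS that can be missing almost only in the roughly 9% who survive, and non-consenting survivors are censored too early in the time-to-death analysis

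*Protocol*

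**What the plan says.** **Missing outcomes.** SAP 6.2.7 sets the rule: "If the proportion of missing data is less than 5% then complete case analysis will be performed". Above 5%, multiple imputation is to be considered. No denominator is named and the primary outcome has no rule of its own. SAP 3.7 defines the population: "The analysis population for the primary outcome (mRS at discharge/30-days) is all" resuscitated, eligible patients attended by a trial paramedic. All trial patients are therefore the natural denominator.

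**Deaths.** Protocol 4.6.1 ("Any patient who does not survive to discharge will automatically be" given a score of six) and SAP 5.1 ("All trial patients who do not survive to hospital discharge (or 30" days) both score death by rule. Protocol 4.6.2 puts survival to discharge at 9%.

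**Consent.** SAP 3.1 reports approval to retain data up to approach as well "as mRS at hospital discharge or death for all patients regardless of whether they consent", and Protocol 4.6.1 expects close to complete ascertainment. Under option C in Protocol 9.7.1, however, "with this option no further data collection will take place". Protocol 5.5 ends the trial for these patients straight after approach, and SAP 3.1 repeats the no-further-data option.

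**Time to death.** SAP 6.2.2 says: "Times will be censored at last contact for" patients known to be alive then. SAP 5.4 has a different rule for survivors to discharge who "did not consent to active or passive follow-up (i.e. censored at ICU discharge for analysis").

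**The concern.** A 5% rule is harmless when any patient might be missing and the missing patients resemble the rest. Neither holds here. About nine patients in ten have an outcome fixed by death, and they fill the denominator without being able to add to the numerator. The patients who can be missing are nearly all survivors, and only survivors can score 0-3. Complete-case analysis then removes patients almost wholly from the group that supplies the good outcomes.

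There is no backstop. The three sensitivity analyses in SAP 6.2.6 change the airway-attempt restriction, the grouping, or the inclusion of non-resuscitated patients. None varies the missing mRS. If missingness differs between arms, SAP 6.2.7 asks only that reasons be explored.

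The SAP expects some missing scores: the Figure F6 footnotes reserve a count for them. The documents also give sites conflicting instructions for one group. Protocol 9.7 has consent usually sought soon after ICU discharge, before the discharge mRS is due. A patient who then chooses option C is covered both by a ban on further collection and by a statement that discharge mRS is obtained regardless of consent.

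**Working it through.** **1. The plan's own sample size.** Inputs from Protocol 4.7: 8% versus 10%, 5% significance, 90% power, ICC 0.005, 7 patients per paramedic. The two-proportion formula with continuity correction gives 4,401 per group (plan: 4,400). The design effect is 1 + (7 − 1) × 0.005 = 1.03, and 4,401 × 1.03 rounds up to 4,534 (plan: 4,535). The plan reproduces. For the power figures below, the effective size is 4,535 / 1.03 ≈ 4,403 per arm.

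**2. What the threshold permits.** 0.05 × 9,070 = 453.5, so 453 missing scores still fall below 5%.

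| Survival to discharge | Source | Survivors | 453 as share of survivors |
|---|---|---|---|
| 9% | Protocol 4.6.2, 4.7 | 816 | 55.5% |
| 10% | Protocol 4.3.4 (about 90% die) | 907 | 49.9% |
| 7% | Protocol 2, low end of UK range | 635 | 71% |

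Applied to survivors at 9%, the same 5% is reached at 0.05 × 816 ≈ 41 missing scores, which is 0.45% of all patients.

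**3. Equal proportional loss.** Let p be the true good-outcome rate and f the share of good outcomes lost (assumption: all missing scores are good outcomes). The fraction of the arm missing is m = fp and the observed rate is (p − m)/(1 − m). The observed odds are p(1 − f)/(1 − p), so an equal f cancels from the odds ratio. At the rule's limit, f = 0.5544:

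- Intubation: m = 0.0444, observed (0.08 − 0.0444)/0.9556 = 3.7%.
- i-gel: m = 0.0554, observed (0.10 − 0.0554)/0.9446 = 4.7%.
- Overall missing 4.99%. The odds ratio stays at 1.28. Power falls from about 91% to about 61%.

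**4. Loss that differs by arm.** Assumptions: no true effect, 9% survival in both arms, all survivors score 0-3, and 10% of survivors missing in one arm against 20% in the other.

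- m = 0.10 × 0.09 = 0.009 and 0.20 × 0.09 = 0.018; overall 1.35%, about 122 of 9,070, far below 453.
- Observed (0.09 − 0.009)/0.991 = 8.17% and (0.09 − 0.018)/0.982 = 7.33%.
- False difference 0.84 points; odds ratio 0.80/0.90 = 0.89 where the truth is 1.
- The standard error at effective sizes 4,363 and 4,324 is about 0.57 points, so the expected z is about 1.47. The chance of a two-sided p < 0.05 is about 31%.

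**5. Time to death, rules side by side.**

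- Non-consenter who dies after ICU discharge but before hospital discharge: SAP 5.4 takes the death date from Form W2 and counts the event. Deaths after hospital discharge also come from Form W2, with no consent condition.
- Non-consenter alive at hospital discharge/30 days: SAP 5.4 censors at ICU discharge, an earlier date than the one at which the patient is known to be alive.
- The 72-hour derivations in SAP 5.4 use the discharge/30-day mRS date to recover patients censored too early, so a later known-alive date is in the data set.

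Whether a non-consenter stays in the risk set after ICU discharge thus depends on whether that patient later dies. The censoring is informative, and it overstates mortality after ICU discharge. The documents give neither the number declining nor later mortality, so no size is attached.

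**The case against.** The strongest reply is that little primary data should be missing. Protocol 4.6.1 plans close to complete ascertainment, Protocol 9.2 seeks approval to collect outcomes to discharge, and SAP 3.1 keeps the discharge mRS whatever the consent. Outcome, consent and follow-up staff are blinded, and patients are likely to remain unaware of allocation, so a large gap between arms is not expected. This stands: 453 is what the rule allows, not what will happen.

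Several stronger readings are tempting, and the documents do not support them:

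- *Feasibility consent shows 14% of survivors will lack the primary outcome.* The 86% in Protocol 5.12 is consent to follow-up at 3 months, not availability of discharge mRS.
- *Non-response within 28 days removes the primary outcome.* That rule (Protocol 9.7.1, 9.7.2) covers people already discharged, when the discharge mRS has already fallen due. Only option C chosen in hospital conflicts with the stated approval.
- *Any loss among survivors biases the result.* Equal proportional loss leaves the planned odds ratio essentially unchanged.
- *Only survivors can be missing.* SAP 5.4 allows survival status itself to be missing, so an unlinked patient who died could lack an mRS.
- *A false effect near the 2-point target could arise.* Missingness of 2% versus 4% of all patients would give 7.14% versus 5.21%, about 1.9 points. But this means 22% versus 44% of survivors without a score, and nothing suggests such a gap.

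The reply does not defend the threshold. If ascertainment is as good as planned, a survivor-based rule costs nothing. If it is not, the present rule would not react.

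**Conclusion.** The concern holds as a mismatch between a generic rule and this outcome. Below 5% of all patients, up to 453 scores, about 50-56% of survivors at 9-10% survival, could be missing without imputation or a sensitivity analysis. This rests on the all-patient denominator, which is the natural reading but not stated text, and on the planned 9,070 patients.

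A reader might infer that the primary result is in danger. The documents do not show that: equal loss costs only power, bias needs loss that differs by arm, and near-complete collection is planned. The 10% versus 20% example shows only that a moderate imbalance, invisible to the 5% rule, is enough to matter.

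The option C wording conflicts with the stated approval and needs reconciling. The censoring rule in SAP 5.4 contradicts SAP 6.2.2 and is informative as written; it affects a secondary analysis and its size cannot be derived from the documents. Overall this is a low-cost safeguard, not a demonstrated threat to the primary result.

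**What to change.** - **SAP 6.2.7:** compute and report primary-outcome missingness by arm among patients alive at discharge/30 days, and apply the 5% threshold to that denominator (about 41 patients at 9% survival). Report patients of unknown survival status separately. When the threshold is exceeded, impute mRS among known survivors.
- **SAP 6.2.6:** add a best/worst-case sensitivity analysis for missing mRS, by arm.
- **Protocol 9.7.1 and 5.5, SAP 3.1:** reconcile the option C wording with the stated approval to collect discharge mRS regardless of consent, so that sites have one instruction.
- **SAP 5.4:** censor non-consenting survivors at the last date known alive, at least the discharge/30-day mRS date, in line with SAP 6.2.2.

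The cost is SAP wording, one protocol clarification and a short additional analysis. No new data are needed.
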